⁷ Diabetes Survival Skills such as taking medication, administering insulin, managing diet, blood glucose monitoring, sick day and hypo- and hyperglycemia management are considered basic skills needed for survival by all patients with diabetes. At a minimum, incarcerated persons transitioning to the community have a critical need for DSS. The purpose of this study is to examine the feasibility and acceptability and preliminary efficacy testing of a 6-session Diabetes Survival Skills(DSS) intervention to incarcerated persons with diabetes within 6-9 months of transitioning to the community. In one facility, the Diabetes Survival Skills sessions will be followed by a support group(DSS+) and feasibility of the support group will be examined.

Research questions: The general research questions for this feasibility study were developed based upon Orsmond and Cohn⁸ proposed questions to guide a feasibility study.

1. How appropriate are the data collection procedures and outcome measures for the intended population and purpose of the study?
2. Are study procedures and intervention suitable for and acceptable to participants?
3. Does the research team have the resources and ability to manage the study and intervention?
4. Does the intervention show promise of being successful with the intended population?

1. The primary aim is to evaluate feasibility of the experimental protocol.

Hypotheses: H1) Recruitment: 96 eligible persons will consent to participate in the study within 2 months after the onset of recruitment H2) Attendance/Attrition: 90% of enrolled participants will attend and complete the 6-session DSS Training. H3) Engagement: 75% of enrolled participants' will document responses to work-book questions, record blood glucose and if applicable associated diet or activity information. H4) Intervention implementation: The intervention will be delivered according to the DSS timeline (Figure1) and session outline. H5) Skill proficiency: Participants will return demonstrate how to use the blood glucose meter, insulin pen (as indicated), and blood glucose log, and other skills specific to DSS session 1-6.

2. The secondary aim of this study is to determine participants' acceptability of the program and program and study materials including the perspective in participating in the intervention using focus groups.

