Design: The proposed study will examine the feasibility, acceptability and preliminary efficacy measures of a quasi-experimental non-equivalent control group 6-week intervention study with repeated measures at baseline, 6 weeks, and 12 weeks. Acceptability of the DSS intervention will be examined using a qualitative descriptive design with focus group interviewing.

Prior to data collection, IRB approval from the University of Connecticut and the CDOC Research Advisory Council (RAC) will be obtained. Procedures for the recruitment of inmates with diabetes will be determined in collaboration with the Connecticut Department of Corrections administration (CDOC). Recruitment procedures as described in the prior section have been previously used and approved by the CDOC RAC. The final RAC approval has been obtained (see Connecticut department of Corrections letter of approval). The RAC has reviewed this proposal and granted approval. After UCONN IRB and RAC approval, meetings with the Wardens will be arranged, email communication will be sent to Correctional Managed Healthcare (CMHC) nursing director (Attachment 2), recruitment flyers will be posted in the participating prisons, and the researcher will negotiate dates and times to be available during several Chronic Care Clinic sessions for in person recruitment as described in the recruitment procedures.

The "sick slips" from inmates requesting to hear more about the study will be collected from my assigned mailbox in medical records or another designated location and subsequently reviewed. Prior to scheduling a meeting with the potential participant, the PI will request that the DOC liaison or other designee review the list of potential participants to confirm that the participants meet the secure

classification to participate in groups. If interested potential participants do not meet the security classification, the PI will follow the DOC procedure for notifying participants who do not meet the DOC classification criteria.

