After the potential participant consents to participate and signs the informed consent, the participant will be asked to complete the demographic survey (Attachment 7), the Health Literacy screening (Attachment 8) and the Montreal Cognitive Assessment, a measure of cognitive function (Attachment 9). If the participant is not able to recall his medications and if the participant has consented to allowing the PI to access the medical or pharmacy record, the PI will arrange to obtain a list of the participant's actual medications from the medical or pharmacy record. A HIPAA release form will be signed if needed after completion of demographic survey. Obtaining informed consent and baseline demographic and cognitive measures will be considered visit 1 for participants from the treatment and control facilities.

For the first two sessions (Group 1 First 48 participants) (Figure 1)The PI will screen potential participants until 48 participants are consented, and enrolled. Twenty-four participants in the designated Treatment facility (Cybulski Correctional Institution)divided into 2 groups of 12 will participate in the same DSS intervention on two separate occasions. Participants (n=24) in the Control facility (Osborn Correctional Institution) will receive the intervention upon completion of week twelve measurements. Figure 1 outlines the schedule for the informed consent, DSS intervention sessions, quantitative assessments and focus groups. As noted in the legend for figure 1. the Control group will receive the intervention after week 12 if they choose to do so.

The PI will begin screening, recruitment and informed consent procedures for Group 2 (the second set of 48 participants) when Group 1 (first 48 participants) completes Visit 4 (approximate start time) (Figure 1). Group 2 (n=24) in the control facility and n=24 in the treatment facility) will begin the DSS sessions and measurement schedule following the same procedures used for Group 1 and as described in Figure 1 Visits 2- 10. The support group is optional for those in the treatment facility because this aspect of the study is being evaluated after the DSS education sessions and three measurement intervals have been completed.

		Visit 1 Week 1 1.5 hours	Visit 2 Week 4 1.5 hours	Visit 3 Week 5 1 hour	Visit 4 Week 6 1 hour	Visit 5 Week 7 1 hour	Week 6 Week 8 1 hour	Visit 7 Week 9 1.5 hours	Visit 8 Week 11 2 Hours	Visit 9 Week 15 1 hour	Visit 10+ 1 hour/week Optional

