At the beginning of each group session, confidentiality guidelines and group expectations will be addressed and clearly stated by the student investigator at every group session. Group members will be told of the importance of maintaining confidentiality and that "what is shared in the group remains in the group" and any information shared in groups should not be discussed outside the group. This will be discussed with every group at the beginning of each session. Confidentiality guidelines will also be posted on a flip-board chart so it is visible for everyone to see and remember at every group session. Reminders not to discuss group topics outside the group will be reiterated at the end of the group session. These procedures will be maintained; however, confidentiality cannot be guaranteed

The PI will also remind the participants at the beginning of each session that she will be taking notes related to diabetes related questions or concerns.

Additionally, at the beginning of each group session members will be told what will happen if the student investigator is informed of self-harm intent and the obligation to refer the member to seek help from their healthcare provider. Since inclusion criteria selects only inmates who are preparing for release from prison this risk of self-harm is minimal but still needs to be identified and addressed.

The only limit to privacy is related to the lack of anonymity to the PI. However, as healthcare professionals the PI will be obligated to adhere to HIPAA guidelines and confidentiality guidelines of the group. The PI will adhere to the standard of confidentiality of group process and group sharing.

For session content, please refer to the intervention protocol (Attachment 15)

During the last thirty minutes of the 90 minutes scheduled for the last session, they will complete the 4 surveys. The PI will read all surveys aloud and collect the surveys after completion. All participants will be invited to participate in the audio recorded focus groups scheduled 2 weeks' post DSS sessions to evaluate acceptability of the DSS intervention. At the 6 week post DSS follow-up to complete questionnaires, the participants will receive a certificate of participation and be thanked for their time.

Focus Group Interviews

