3. **Cognitive function** will be measured by the Montreal Cognitive Assessment (MoCA)²(Attachment 9) is designed as a rapid screening instrument for mild cognitive dysfunction. It assesses different cognitive domains: attention and concentration, executive functions, memory, language, visuoconstructional skills, conceptual thinking, calculations, and orientation and takes approximately 10 minutes to administer. The total possible score is 30 points; a score of 26 or above is considered normal. Internal consistency of the MoCA ranges from 0.72 – 0.83. Cronbach's alpha in geriatric, mixed clinical population and stroke and vascular dementia populations.

4. Feasibility measures Aim1: Feasibility will be evaluated with recruitment and enrollment tracking forms, attendance sheets, field notes, adherence to intervention manual, participant workbook entries, glucose meter procedure manual, and blood glucose logs to obtain data needed to support hypotheses. Reliability of all instruments will be evaluated.

5. Acceptability measure Aim 2: Data will be obtained using an IRB approved FGI guide e.g. probes such as perspective about the overall quality of the program? Or how well did the program prepare you for transitioning to the community?**Preliminary Efficacy measure: Dependent Variables:**

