- 1) frequency of the monitoring
- 2) who will conduct the monitoring (Under UConn policy a student cannot be the sole person responsible for monitoring the data and safety of the protocol procedures.)
- 3) what data will be monitored
- 4) how the data will be evaluated for problems?
- 5) what actions will be taken upon the occurrence of specific events or end points
- 6) who will communicate to the IRB and how communication will occur

Sample response to issues listed above for minimal risk/slight increase over minimal risk – “Survey results will be monitored by the PI in conjunction with the student investigator once every two weeks (items 1, 2 and 3). Survey responses will be reviewed to monitor for clarity (i.e., the same question is skipped by 5 or more participants). In that case, the question will be revised and an amendment will be submitted to the IRB (items 4, 5 and 6).”

The PI, [name] PhD, will oversee the study procedures for data acquisition and validation. Survey results will be monitored by [name] once a month until completion of the study. Survey responses and audio transcripts will be reviewed to monitor for clarity. If a problem is noted with data clarity, the question will be revised and an amendment will be submitted to the IRB. Data safety is assured through: 1) a common core of conjoint training and routinely scheduled fidelity monitoring; 2) continuous team (agency & faculty) feedback through weekly and monthly meetings with telephone and email communication as needed; and 3) final data editing and entry at UCONN School of Nursing; Any paper forms are retained in a locked file in at UConn Center for Nursing Scholarship locked file with access provided only to those who are involved in the project. Computer files are password protected on faculty computers. Access provided only to those working on the project. Any variation from protocol will be corrected within two days and reported to the IRB within the same week.

Privacy/Confidentiality

Explain how the privacy interests of participants will be maintained during the study (note that privacy pertains to the individual not to the data). Describe procedures for protecting confidentiality of data collected during the study and stored after study closure. Describe how data will be coded. Describe plans for storage and security of electronic data (plan must comply with the University's Policy on the

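### The monitoring plan's rule to reword unclear survey questions does not exempt the four outcome scales, so the repeated measures could mix versions of a scale.

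*Combined protocol and SAP*

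**What the plan says.** Section VII, Data Safety Monitoring, has survey results monitored by the investigator "once a month until completion of the study". It adds: "Survey responses and audio transcripts will be reviewed to monitor for clarity". The action follows directly: "If a problem is noted with data clarity, the question will be revised and an amendment will be submitted to the IRB". This is the investigator's own plan; the sample answer printed in the form stands before it.

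That section does not list the instruments. The Intervention text says of the last session that "they will complete the 4 surveys", meaning SKILLD, SCODI, OEQ and PAID, and Figure 1 lists the same four under surveys at Measures 1, 2 and 3. The design has "repeated measures at baseline, 6 weeks, and 12 weeks", and Aim 3 is analysed by repeated-measures ANOVA (Statistical strategy).

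Two other statements bear on the same scales. Research question 1 asks: "How appropriate are the data collection procedures and outcome measures for the intended population and purpose of the study". Under Measures, item 4, the plan states: "Reliability of all instruments will be evaluated".

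**The concern.** A repeated-measures comparison assumes that the same instrument is used each time. As written, the rule lets an item of an outcome scale be reworded while participants are between measures. Part of a change in score could then come from the wording and not from DSS. The reliability and scoring cited under Measures belong to the existing wording and would not carry over automatically to a changed item.

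The trigger is plausible here. Low reading ability is expected (Capacity to Consent), cognitive dysfunction is described as often present (Introduction), and the reliability quoted for SKILLD runs from 0.54 to 0.72, with 0.65 in incarcerated persons. The trigger is also loose: the form's sample answer uses a count of five or more participants skipping a question, whereas the adopted text needs only that a problem is noted.

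Research question 1 is also touched. An unclear item is itself a finding about whether the measures suit this population. Rewording it part-way through leaves less evidence on either version.

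**Working it through.** **1. The plan's own figure.** Inputs from Justification of Sample Size: d = 0.50 (f = 0.25), alpha 0.05, power 0.80, 2 groups, m = 3 measures, correlation 0.50. For the between-groups effect, lambda = f² × N × m / (1 + (m − 1) × rho). With N = 86, lambda = 0.0625 × 86 × 3 / 2 = 8.06 on 1 and 84 degrees of freedom, which gives power 0.801. The stated 86 is reproduced, and 86 / 0.90 = 95.6, so 96. The group-by-time version would need only 28. The planned d of 0.50 is therefore a difference between facilities, which matters in step 4.

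**2. Timing.** Figure 1 puts Measures 1, 2 and 3 at Weeks 4, 9 and 15.
- Gaps: 9 − 4 = 5 weeks and 15 − 9 = 6 weeks. A month is about 4.3 weeks, so a monthly review falls inside each gap.
- Group 2 recruitment starts "when Group 1 (first 48 participants) completes Visit 4", which is Week 6 in the treatment schedule. Baseline comes 4 − 1 = 3 weeks after Visit 1, so Group 2's baseline falls at about Group 1's Week 6 + 3 = 9, or later.
- In the control schedule Visit 4 is Week 15. If each facility counted its own visits, Group 2's control baseline would come at about Week 15 + 3 = 18.

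**3. Points per item.**
- SKILLD: 100 / 10 items = 10 points.
- PAID: 4 × 1.25 = 5 points at most.
- Assumption: rewording one SKILLD item changes the proportion correct by 0.1 to 0.5. The mean then moves by δ = 1 to 5 points with no change in knowledge.
- Assumption: one PAID item moves by 0.5 to 2 points. The score then moves by 0.6 to 2.5 points.

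**4. Where δ goes.** Each facility has 24 men in Group 1 and 24 in Group 2.
- *Problem found at Group 1's baseline, new wording in use by Week 9 in both facilities.* Group 1 answers old, new, new; Group 2 answers new throughout. Bias in a facility's pooled change from Measure 1 to 2: (24 × δ + 24 × 0) / 48 = δ/2, or 0.5 to 2.5 SKILLD points. Between facilities: δ/2 − δ/2 = 0 if the wording acts equally in both.
- *Problem found at Group 1's Measure 2, new wording in use by Week 15 in both facilities, and Group 2's baseline already taken on the old wording.* Both cohorts go from old to new by Measure 3, so the within-facility change is biased by δ. Between facilities: δ − δ = 0 under the same condition.
- *The same, but Group 2 in the control facility starts at about Week 18.* Control Group 2 answers new throughout, so the control bias is δ/2 against δ in the treatment facility. The contrast is biased by δ − δ/2 = δ/2.

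**5. Safeguards.** The sections on Measures, Design, Statistical strategy and Data Safety Monitoring contain no exemption for the four scales, no delay of revision until after Measure 3, no record of versions and no analysis rule for mixed versions.

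**The case against.** The strongest reply is that the text commits to much less than a reader might infer. Four points stand.

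- **Not named.** The monitoring section does not mention the outcome scales. The protocol also calls the demographic form a survey, and audio transcripts are reviewed in the same sentence, so the question to be revised could be a demographic or focus-group item. A reader might infer a deliberate plan to rewrite SKILLD or PAID; the text does not show one. It does include survey responses and leaves the scales unprotected.
- **Not automatic.** A monthly review is not a monthly change. A problem must be noted, and item 3 of the Principal Investigator Certification requires IRB approval before the protocol is amended. With gaps of 5 and 6 weeks, approval could come too late to matter. Approval would not, however, make two versions comparable.
- **Not the only action rule.** The same section has departures from protocol corrected within two days and reported within the week. That rule does not prevent an approved rewording.
- **Not a bias to set against d = 0.50.** A 3-point SKILLD shift is 3/25 = 0.12 to 3/15 = 0.20 SD for an assumed SD of 25 to 15, and it is tempting to subtract this from the planned effect. But it is a shift in one group's mean, while 0.50 is a difference between facilities. If both prisons switch together and the wording acts equally, the contrast is unaffected.

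It is also fair to say that checking item clarity is part of a feasibility study's purpose, and that SKILLD items can be analysed singly, so a changed item could be isolated. Both support monitoring and logging. Neither requires rewording before Measure 3.

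**Conclusion.** The point holds as a conditional risk. If a clarity problem were found in one of the four scales and a rewording were approved before Measure 3, within-group change and the reliability estimates would mix versions. Under the assumed 1 to 5 point effect of one reworded SKILLD item, pooled within-facility change would be off by 0.5 to 5 points of 100, depending on when the switch came. The between-facility contrast would be off only if the switch or its effect differed by facility.

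The size of any wording effect is assumed; the documents give no figure. The conclusion also assumes that the monitoring rule uses the word survey as the Intervention text and Figure 1 do. The impact is modest: the scale comparisons serve the tertiary, exploratory aim, the protocol itself calls efficacy testing limited, and H1 to H5 and the focus-group findings do not rest on these scores. The documents do not support a reading that the efficacy comparison is invalid as planned. The change is worth making because the present rule is open-ended and the remedy is cheap.

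**What to change.** In Data Safety Monitoring, replace the general revision rule with these provisions:

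- Revision during the study is limited to study-made material: the demographic survey, the focus group guide and the workbook.
- The wording and scoring of SKILLD, SCODI, PAID and OEQ stay fixed for all participants through Measure 3.
- Any clarity problem with these scales is logged by item, facility and measure. The log is reported under research question 1 and used to choose or adapt measures for the follow-on pilot.

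This takes a sentence or two, with no change to sample size, visits or analysis. The downside is that a confusing item stays in use until the study ends. The investigator already reads the surveys aloud, so participants who have trouble reading still hear every item.
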